9.1.4. Additional Analysis of IARs

Additional summary tables/plots will be provided to describe the clinical characteristics of the IARs by treatment group, including the event rates, changes in severity over time, and time to first IAR.

9.1.4.1. Analysis of Time to First IAR-TEAE

This calculation is only performed for subjects who have IARs. For these subjects, the time (in weeks) from the first dose of study drug to the onset of the first TEAE that is an IAR (ie, IAR-TEAE) will be calculated for each subject as:

$$\text{Time to first IAR-TEAE (Weeks)} = (\text{date of the first IAR-TEAE} - \text{date of first dose of study drug} + 1) / 7.$$

The calculated times will also be presented in a subject listing.

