9. ANALYSIS OF SAFETY

Safety will be evaluated through the analyses of AEs, clinical safety laboratory data, vital signs, physical examination, electrocardiogram (ECG), and concomitant medications.

Safety analyses will be based on the safety population. Safety data will be summarized using counts and percentages for categorical data and using descriptive statistics (n, mean, SD, median, Q1, Q3, minimum, and maximum) for continuous data. No formal statistical tests will be performed.

Infusion-associated reactions in the ATB200/AT2221 arm will be compared in frequency to the alglucosidase alfa/placebo arm in this study.

Adverse events will be coded by system organ class (SOC) and preferred term (PT) using MedDRA version 20.1 or higher.

Concomitant medications and nondrug therapies will be summarized by treatment group. Concomitant medications and nondrug therapies will be coded using WHO DDE, March 2017 or later.

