9.1.3. TEAEs Reported as Infusion-associated Reaction

For any AE, the reporting investigator is requested to enter on the AE eCRF whether the AE is deemed to be an infusion-associated reaction and determine the relationship to each of the study drug components (ATB200, AT2221, alglucosidase alfa, and placebo).

To further characterize TEAEs considered by the reporting investigator to be IARs, a summary table of TEAEs reported as IARs will be provided. The number and percentage of subjects who experienced IARs will be presented by SOC and by PT within SOC for each treatment group. A subject will be counted only once within the same SOC and within the same PT.

Summary of IARs will also be presented by severity, and for relationship to each treatment component (ATB200, AT2221, alglucosidase alfa, and placebo) as well as for the co-administration. Additional summary tables/plots will be provided to describe the clinical characteristics of the IARs by treatment group, including the event rates, changes in severity over time, and time to first IAR (see Section 9.4.1). The IAR summary will also be presented by prior history of IARs (yes/no), and by ERT status (experienced/naïve).

A listing of treatment-emergent IARs, serious IARs, IAR-related deaths, and IARs leading to study drug discontinuation will be provided. A listing displaying the summary of number of infusions and infusions associated with IARs by each individual subject who had an IAR will also be provided. For each subject, this listing provides subject ID, number of infusions received, number of infusions associated with IARs, percentage of infusions associated with IARs, the TEAEs that are IARs (IAR-TEAEs) occurring in each of the time intervals (see Section 9.1.4.2 and Section 9.1.4.3), and the event severity of the IARs corresponding to (or associated with) each infusion.

A summary of IAR-TEAEs by subjects with IARs, and the number of subjects with 1, 2, 3, 4 to 6, 7 to 10, 11 to 19, and ≥ 20 IARs will be summarized for each treatment group. A summary of the number of infusions and IARs associated with the infusions will be provided for all subjects as well as only for subjects who had IARs.

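### Time to first IAR is summarised by arm only among subjects who had an IAR, so the plan has no display of first-IAR timing across all treated subjects

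*SAP*

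**What the plan says.** SAP Section 9.1.4.1 defines time to first IAR in weeks as (date of first IAR − date of first dose + 1)/7 and restricts it: "This calculation is only performed for subjects who have IARs". The times also go into a subject listing. Section 9.1.4 places the result in tables or plots "by treatment group, including the event rates, changes in severity over time, and time to first IAR". For this summary the SAP specifies no censoring rule, Kaplan-Meier curve or cumulative incidence.

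Other planned IAR output bears on the point:

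- Section 9.1.3: "The number and percentage of subjects who experienced IARs will be presented by SOC and by PT within SOC for each treatment group". It also counts, by arm, "the number of subjects with 1, 2, 3, 4 to 6, 7 to 10, 11 to 19, and ≥ 20 IARs", and adds an infusion-level summary: "A summary of the number of infusions and IARs associated with the infusions will be provided for all subjects".
- Section 9: "Infusion-associated reactions in the ATB200/AT2221 arm will be compared in frequency to the alglucosidase alfa/placebo arm in this study". On safety generally: "No formal statistical tests will be performed".
- Section 9.1.4.2: event rates by onset interval, from days 1–3 to beyond 12 months, for each arm. These cover all IARs, not first IARs.
- Section 3.3.6: the safety endpoint is IAR frequency and severity. Time to first IAR is not named there.

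**The concern.** A subject treated for a year without a reaction contributes nothing to the Section 9.1.4.1 summary. The two arms are therefore shown side by side in sets chosen by what happened after treatment began. Reactors in one arm may differ from reactors in the other. That is a possible selection effect, and nothing in the documents shows that it occurs.

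IARs matter here because Protocol Section 6.1 describes them as the most serious tolerability problem of the comparator. A reader who sees similar reactor-only times in the two arms could take this as similar tolerability, when the figure carries almost no information on risk. The share of subjects still IAR-free at a given time, by arm, cannot be read from it. Protocol Section 11.1 itself refers to six months free of IARs when it describes eligibility for home administration, so IAR-free time is a quantity that the trial uses.

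**Working it through.** Section 9.1.4.1 states no figure to reproduce. The check asks what a reactor-only summary can show.

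**Inputs from the documents.** Treatment lasts 52 weeks (Protocol synopsis). About 110 subjects are randomized 2:1 (SAP 4.3), which is about 73 and 37. The only IAR risk given is 6 of 21 subjects, or 29%, in the earlier open-label study over 18 months (Protocol 6.3.5).

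**Assumptions.** The documents give no per-arm IAR risk for this trial. Risks of 10% to 50% and a constant hazard are illustrative.

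**Step 1: what is conditioned away.** Let F(t) be the cumulative incidence of a first IAR by week t. Among reactors the distribution of onset is F(t)/F(52). If one arm's F is k times the other's at every t, k cancels and the reactor-only distributions are identical. This does not depend on the hazard shape.

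**Step 2: constant hazard.** For 52-week risk p:

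- hazard λ = −ln(1 − p)/52
- mean among reactors = 1/λ − 52(1 − p)/p
- median among reactors = −ln(1 − p/2)/λ

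For p = 10%: λ = 0.002026, and the mean is 493.5 − 468.0 = 25.5 weeks. For 25%: 180.8 − 156.0 = 24.8. For 50%: 75.0 − 52.0 = 23.0.

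| Risk p | Mean among reactors (weeks) | Median among reactors (weeks) |
|---|---|---|
| 10% | 25.5 | 25.3 |
| 25% | 24.8 | 24.1 |
| 30% | 24.5 | 23.7 |
| 50% | 23.0 | 21.6 |

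From 10% to 50% the mean moves 25.5 − 23.0 = 2.5 weeks. From 10% to 30% the median moves 25.3 − 23.7 = 1.6 weeks.

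**Step 3: numbers contributing.** At 10% control and 30% new treatment, reactors number 37 × 0.10 = 3.7 and 73 × 0.30 = 21.9. The control summary would rest on about four subjects.

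**Step 4: information content.** The simulation used 37 vs 73 subjects, 3,000 runs and a two-sided 5% level, with non-reactors censored at week 52. The SAP plans none of these tests; they only gauge how much each summary can show.

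| Control vs new risk | Rank-sum, reactors only | Log-rank, all treated | Fisher, incidence |
|---|---|---|---|
| 10% vs 30% | 4.1% | 68% | 64% |
| 10% vs 40% | 5.5% | 94% | 92% |
| 20% vs 40% | 5.5% | 57% | 53% |
| 20% vs 50% | 6.3% | 89% | 87% |

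The reactor-only column stays close to the 5% false-positive rate. Plain incidence, which Section 9.1.3 already tabulates, recovers nearly all that the log-rank test does.

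**The case against.** The strongest reply is that nothing is hidden. A reader might infer that a large difference in IAR risk would go unseen in the trial's report. The documents do not support that: Section 9.1.3 gives the number and percentage of subjects with IARs by arm, and Section 9 states a comparison of frequency. A 10% versus 50% difference would appear there as 10% versus 50%. A reader might also infer that reactor-only times are offered as a treatment comparison. They are not: the restriction is stated openly, the purpose is descriptive, and safety is untested. Follow-up is nominally 52 weeks with 10% dropout planned, so simple incidence should be close to cumulative incidence, as Step 4 shows. The constant hazard is also unsupported. Protocol 12.2.3 requires extra monitoring after the first three infusions, which suggests that early reactions are the concern.

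Most of this stands and limits the point to one summary. It does not close the gap:

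- Crude percentages do not account for unequal follow-up, and SAP 4.5.1 describes missed infusions, early withdrawals and subjects on study beyond 12 months.
- The onset-interval rates pool first and later IARs and name no denominator still at risk. Protocol 13.1.3 calls for premedication at all remaining infusions after an IAR, so later rates are altered by the first event.
- Early clustering would change the means in Step 2, but not the cancellation in Step 1.

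**Conclusion.** The point holds for this one summary. Reactor-only time to first IAR, shown by arm, is selected on a post-treatment outcome and nearly blind to risk: 2.5 weeks in the mean for a five-fold difference, given a constant hazard and assumed risks. What the plan lacks is the timing of the first IAR in all treated subjects with follow-up accounted for. How often subjects react is covered elsewhere in Section 9. The summary is supplementary, descriptive and outside the named safety endpoint, so this is a minor improvement and no threat to the safety conclusions.

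**What to change.** In SAP Section 9.1.4.1:

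1. Present Kaplan-Meier (cumulative-incidence) time to first IAR from first dose for the whole safety population, by arm and by ERT status, with numbers at risk.
2. Censor subjects without an IAR at one named cut-off after the last infusion. The SAP must choose it, because the documents give no single window. Protocol 13.1.3 has a late-type window of 24 to 96 hours after the infusion ends, and also a sentence covering 24 hours or later with no upper limit. SAP 9.1.1 uses last dose plus 30 days for TEAEs.
3. Keep the per-subject times as the listing, labelled as among subjects with an IAR.
4. Correct the cross-reference in Section 9.1.3. It sends the reader to Section 9.4.1, which covers medication dates; the analysis is in 9.1.4.1.

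The cost is one extra figure and table, descriptive only. The dates of first dose, last dose and IAR onset are already collected.

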9.1.4.2. Analysis of IARs by Onset Intervals

The IARs will also be analyzed by onset intervals categorized as follows:

- 1 to 3 days, 4 to 7 days, 8 to 14 days, 15 to 28 days, 29 days to ≤ 3 months, > 3 months to ≤ 6 months, > 6 months to ≤ 12 months, and > 12 months.

The event rates and changes in severity over time (over these intervals) will be summarized for each treatment group. This analysis will further describe the clinical characteristics of IARs and help determine whether the IARs disappear over time or appear late.

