6.3.5. Safety

Safety and tolerability data in all 21 subjects reflect 18 months of treatment (data cutoff date of August 2018), with 1 subject having received ATB200/AT2221 for over 28 months. Adverse events (AEs) have been generally mild to moderate and transient. ATB200/AT2221 has resulted in a low rate of IARs following more than 900 infusions (8 events of IARs in 6 subjects).

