12.2.3. Infusion Visits and Home Infusion Visits

Infusion visits will be scheduled every 2 weeks for administration of study drug. Changes in the protocol-prescribed duration of study drug infusion due to safety or tolerability issues will be documented in the eCRF. In addition to the assessments noted in [Table 10](#), each site should follow their facility guidelines for performing infusions to monitor vital signs or other safety procedures that may be in place.

At visits through Week 6, additional safety assessments (eg, clinical laboratory tests) will be performed for monitoring of initial safety. In addition, subjects will be monitored for 3 hours after the end of the first 3 infusions (ie, Day 1 and Weeks 2 and 4) by study personnel who are trained in diagnosing and treating acute hypersensitivity reactions and who have immediate access to medication and equipment to treat such reactions. Any additional monitoring according to standards at individual sites should also be performed. Any signs or symptoms noted during or after the infusion should be reported as an AE. All assessments will be performed before infusion of study drug. No efficacy assessments will be performed at these visits.

If consistent with local laws and regulations, subjects may be considered eligible for administration of ATB200/AT2221 at their home. Eligible subjects may request participation in the Home Infusion Program with requests granted on a case-by-case basis following discussion between the Amicus medical monitor and investigator with prior approvals from IRBs/IECs/REBs and regulatory authorities. Home infusions of ATB200 will be performed by a trained home infusion nurse provided by an Amicus designated home infusion service provider. All subjects participating in the Home Infusion Program will be required to complete all functional assessments at the protocol-specified site visits.

Subjects who participate in the Home Infusion Program must meet all of the following inclusion criteria and none of the following exclusion criteria.

Inclusion Criteria:

- Resides in a country where it is permissible to administer alglucosidase alfa outside of a hospital setting
- Meets the following requirements regarding feasibility of the home site for ERT infusion:
 - Availability of sufficient space to prepare and administer ATB200 infusion
 - Availability of utilities and equipment required for storage of study drug upon receipt

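### SAP 9.1.4.2 reads a time trend in IARs from day intervals holding 0 to about 13 scheduled infusions, and does not define the event-rate denominator

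*SAP*

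**What the plan says.** SAP 9.1.4.2 sets the first five onset intervals as "1 to 3 days, 4 to 7 days, 8 to 14 days, 15 to 28 days, 29 days to ≤ 3 months". One interval from 3 to 6 months follows, and the last two are "> 6 months to ≤ 12 months, and > 12 months". On the measure it says: "The event rates and changes in severity over time (over these intervals) will be summarized for each treatment group." The purpose is then given: "This analysis will further describe the clinical characteristics of IARs and help determine whether the IARs disappear over time or appear late."

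The section does not state the time origin, the month length, the denominator of the event rate, or how an IAR is linked to an infusion. Because the intervals run past 12 months, they are read here as time since first dose.

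The neighbouring sections do not answer the same question:

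- SAP 9.1.3 uses infusions as a base, but over the whole study: "A summary of the number of infusions and IARs associated with the infusions will be provided for all subjects", and again for subjects with IARs only. Its listing covers individual subjects who had an IAR. It shows infusions received, the percentage with IARs, and IARs by time interval, but no aggregate rate by time.
- SAP 9.1.4.1 (time to first IAR) includes only subjects who had an IAR, so it has no at-risk denominator.
- SAP 9.1.4.3 concerns hours after the start of an infusion.

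**The concern.** An IAR needs an infusion to react to, so the opportunity for an IAR depends on how many infusions fall in an interval. Here the intervals differ in length and, under a 2-weekly schedule, differ greatly in the number of infusions they contain. Two of them contain none when the subject is on schedule.

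The table is meant to show whether IARs fade or emerge late. If its rate is a count, a percentage of subjects or a patient-time rate, part of the pattern across rows will reflect the schedule. Different choices can point in opposite directions from the same data. The frequency and severity of IARs is a stated safety endpoint (SAP 3.3.6), so this time course is likely to be described in the study report.

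**Working it through.** **Inputs.** Infusions every 2 weeks in both arms (SAP 4.2), through Week 52 (Protocol Table 10). Day 1 is the first dose (SAP 6.2.1). The intervals are those of SAP 9.1.4.2. Its month length is not stated; 30.4 days is borrowed from the exposure calculation in SAP 9.4.2. Cuts at Days 91, 183 and 365 are shown as an alternative.

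SAP 9.4.2's formula for planned infusions gives (365 − 1 + 14)/14 = 27. This matches infusion days 1 + 14k for k = 0 to 26, that is Days 1, 15, 29, …, 365. The SAP gives no numerical result for this analysis, so there is none to reproduce.

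**Step 1: infusions per interval. Step 2: what a constant risk p per infusion would show.** For k infusions in an interval of L days:

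- expected IARs per 100 subjects = 100·k·p
- percentage of subjects with an IAR = 100·[1 − (1 − p)^k]
- patient-time rate relative to the steady schedule = (k/L)/(1/14)

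The table uses p = 2% as an assumption, with all subjects on schedule. The last three columns use the 30.4-day month.

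| Interval | k, 30.4-day month | k, cuts 91/183/365 | IARs per 100 subjects | % of subjects | Relative patient-time rate |
|---|---|---|---|---|---|
| Days 1–3 | 1 | 1 | 2 | 2.0 | 4.67 |
| Days 4–7 | 0 | 0 | 0 | 0 | 0 |
| Days 8–14 | 0 | 0 | 0 | 0 | 0 |
| Days 15–28 | 1 | 1 | 2 | 2.0 | 1.00 |
| Day 29 to 3 months | 5 | 5 | 10 | 9.6 | 1.11 |
| 3–6 months | 6 | 7 | 12 | 11.4 | 0.92 |
| 6–12 months | 13 | 13 | 26 | 23.1 | 1.00 |
| Over 12 months | 1 | 0 | 2 | 2.0 | not meaningful |

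Other month lengths change little. With 365.25/12 days the counts are 1, 0, 0, 1, 5, 6, 14, 0. With 28 days they are 1, 0, 0, 1, 4, 6, 12, 3.

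**Step 3: the apparent trends.**

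- Counts: 13/1 = 13-fold from Days 1–3 to months 6–12, whatever p is. The percentage of subjects rises 23.1/2.0 = about 11.5-fold at p = 2%.
- Patient-time, cuts 91/183/365: Days 1–3 have 1/3 infusion per day. The later intervals up to 12 months have 1/14, 5/63, 7/92 and 13/182. The fall is (1/3)/(5/63) = 4.2-fold to (1/3)/(1/14) = 4.7-fold. With the 30.4-day month, the 3–6 month interval has 6/91 and the upper end becomes (1/3)/(6/91) = 5.1-fold.
- From Day 15 to Month 12, the patient-time rate stays within 1.00 to 1.11 of the steady schedule (0.92 to 1.11 with the 30.4-day month).
- Per infusion, the rate is p in every interval that contains an infusion.

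**Step 4: sensitivity.** Protocol 6.3.5 reports, for the earlier open-label study, a low IAR rate "following more than 900 infusions (8 events of IARs in 6 subjects". Taking p = 8/900 = 0.9% gives 0.9 expected IARs per 100 subjects in Days 1–3 and 100 × 13 × 8/900 = 11.6 in months 6–12, again 13-fold. If the risk truly fell four-fold (assumed: 4% for infusions 1–2, 2% for 3–7, 1% after), counts would still rise from 4 per 100 subjects in Days 1–3 to 13 × 1 = 13 in months 6–12.

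**Step 5: the empty intervals.** Days 4–7 and 8–14 hold no scheduled infusion, but IARs there are possible. A late-type reaction may start up to 96 hours after an infusion (Protocol 13.1.3), so one from Day 1 can start on Days 4–5. The ±3-day visit window also lets the second infusion fall on Days 12–14. For an on-schedule subject, a rate per infusion in these two rows has a zero denominator.

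**The case against.** The strongest reply is that the SAP promises event rates and does not exclude a rate per infusion, which would remove the distortion. A reader might infer that the reported trend will come from the interval widths and not from the drug. The documents do not support that: the denominator is open, and a true change in risk would still contribute to the pattern. Opportunity confounds the trend; it does not wholly determine it. The reply is still incomplete, because even a per-infusion rate does not work in the Days 4–7 and 8–14 rows as drawn.

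A reader might also infer that every other denominator misleads throughout. It does not. Patient-time is nearly undistorted from Day 15 to Month 12, so its problem is confined to the first 14 days, apart from the sparse interval beyond 12 months.

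A further tempting step is to say that detection changes with time, since "subjects will be monitored for 3 hours after the end of the first 3 infusions (ie, Day 1 and Weeks 2 and 4"), and home infusion may come later. The documents do not show differential capture. Protocol 12.2.3 also asks for site-standard monitoring and for reporting of any sign or symptom during or after infusion, and home infusions are given by a trained nurse. The IAR windows in Protocol 13.1.3 apply to all infusions.

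Finally, both arms share the schedule, so contrasts between arms within an interval are largely unaffected, barring different rates of missed infusions or withdrawal. SAP section 9 plans no formal safety tests. These points limit the consequence, but whether IARs fade or emerge late is a question across intervals within an arm, which a shared schedule does not protect.

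**Conclusion.** The concern holds as one of confounding by infusion opportunity together with an undefined denominator. The intervals hold from 0 to about 13 scheduled infusions (maximum 12 to 14 across month conventions). Under constant risk per infusion, counts would be 13-fold higher in months 6–12 than in Days 1–3. A patient-time rate would fall 4.2- to 4.7-fold after Days 1–3 (up to 5.1-fold with a 30.4-day month) and then be nearly flat to Month 12. No other section gives a per-infusion summary by time.

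These figures assume on-schedule infusions, onset counted from first dose, and an illustrative risk per infusion. The 2% and the falling-risk scenario are assumptions, and the 0.9% comes from another study; none predicts this trial. The 13-fold ratio for counts and the patient-time ratios do not depend on the risk chosen. No hypothesis test or efficacy claim is affected. The change is worth making because the SAP gives this table an interpretive purpose that it cannot serve as specified.

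**What to change.** In SAP 9.1.4.2, assign each IAR to its triggering infusion. Report by arm the IARs per 100 infusions administered and the percentage of infusions with an IAR, with severity, by infusion-number band: for example 1, 2, 3, 4–7, 8–14, 15–27 and above 27. On schedule, infusions 7, 14 and 27 fall on Days 85, 183 and 365, so the later bands keep roughly the present quarterly and half-yearly cuts. Unequal bands do no harm once infusions are the denominator. Showing the number of subjects infused in each band lets the reader see attrition.

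Alternatively, keep the day intervals with Days 1–14 merged, use infusions administered in each interval as denominator, and state the month length and time origin.

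The cost is a few lines of SAP text and one revised table shell. Infusion counts and the link from IAR to infusion are already needed for the SAP 9.1.3 summary and listing, so no new data are required. A split by site and home infusion is not needed for this point.
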